9.1 Definition and Selection of Statistical Analysis Datasets

All statistical tests shall employ two-tailed procedures, with $p < 0.05$ indicating statistically significant differences.

Quantitative indicators shall be described by calculating mean, standard deviation, maximum, minimum, and median values. Categorical indicators shall be described by case numbers and percentages within each category. All data processing shall be conducted using SPSS professional statistical software.

Comparisons between groups for general characteristics were analysed using appropriate methods according to indicator type. Inter-group comparisons for quantitative data employed paired t-tests (assuming equal variance and normal distribution) or Wilcoxon signed-rank tests based on data distribution; intra-group comparisons used paired t-tests (assuming normal distribution) or Wilcoxon signed-rank tests. Categorical data will be analysed using chi-square tests or exact probability methods (where chi-square is inappropriate); ordinal data will be analysed using Wilcoxon signed-rank tests or Cochran-Mantel-Haenzel (CMH) tests.

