The inferior frontal cortex (IFC) is closely associated with OCD's characteristic functions of response inhibition, conflict resolution, and uncertainty processing. Research indicates that cognitive behavioural therapy (CBT) can alter IFC volume. This study aims to explore the efficacy of repetitive transcranial magnetic stimulation (rTMS) using novel, individualized IFC targeting combined with symptom-induction techniques.

Reference

- 1 Hirschtritt, M. E., Bloch, M. H. & Mathews, C. A. Obsessive-Compulsive Disorder: Advances in Diagnosis and Treatment. *Jama* 317, 1358-1367, doi:10.1001/jama.2017.2200 (2017).
- 2 Sinai, A. et al. Focused Ultrasound Thalamotomy in Tremor Dominant Parkinson's Disease: Long-Term Results. *J Parkinsons Dis* 12, 199-206, doi:10.3233/JPD-212810 (2022).
- 3 Yamamoto, K. et al. Focused Ultrasound Thalamotomy for Tremor-dominant Parkinson's Disease: A Prospective 1-year Follow-up Study. *Neurol Med Chir (Tokyo)* 61, 414-421, doi:10.2176/nmc.oa.2020-0370 (2021).
- 4 Grant, J. E. Clinical practice: Obsessive-compulsive disorder. *N Engl J Med* 371, 646-653, doi:10.1056/NEJMcp1402176 (2014).

5 Banks, G. P., Heilbronner, S. R., Goodman, W. & Sheth, S. A. A population-normalized tractographic fiber atlas of the anterior limb of the internal capsule: relevance to surgical neuromodulation. *J Neurosurg* 137, 1278-1288, doi:10.3171/2022.1.JNS211935 (2022).

6 Bonelli, R. M. & Cummings, J. L. Frontal-subcortical circuitry and behavior. *Dialogues Clin Neurosci* 9, 141-151, doi:10.31887/DCNS.2007.9.2/rbonelli (2007).

II. Research Objectives and Anticipated Outcomes

- (1) To validate the efficacy of 20Hz rTMS targeting the right IFC in treating treatment-resistant obsessive-compulsive disorder (OCD);
- (2) To investigate whether provocation techniques for obsessive symptoms can enhance treatment efficacy;
- (3) To explore the effects of transcranial magnetic stimulation on cognitive function in OCD patients and its potential physiological mechanisms.

III. Research Content and Methods

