3.1 Overall Study Design and Plan

This study constitutes an open-label, prospective, single-centre investigation.

The intervention employs 20Hz repetitive transcranial magnetic stimulation (rTMS) targeting the right inferior frontal cortex (rIFC). To shorten the treatment cycle, reduce dropout rates, and ensure efficacy, the study will employ the following design: six stimulation sessions per day for five consecutive days, totalling 30 therapeutic stimulation sessions. Magnetic resonance imaging (MRI) scans, cognitive function assessments, and symptom evaluations will be conducted before and after the intervention. Symptom follow-up assessments will occur at two weeks post-treatment, with both symptom and cognitive function follow-ups at four weeks post-treatment. Symptom assessments will be completed by psychiatrists (psychiatrists/psychologists), while the intervention will be administered by trained research assistants.

The study aims to investigate the cognitive regulatory effects of non-invasive interventions. Participants will undergo tailored cognitive assessments based on

individual clinical profiles, with all tasks completed via computer using keyboard or mouse input. These tasks primarily evaluate working memory whilst also assessing attention, learning and memory, executive control, reasoning ability, risk decision-making, affective decision-making, and emotional awareness. Additionally, neuroimaging techniques will be employed to investigate the neural mechanisms underlying cognitive function in OCD patients. Participants will undergo task-related functional magnetic resonance imaging (fMRI) before and after electrical stimulation, performing a series of cognitive tasks related to executive function and affective decision-making during scanning. This will enable comparison of rTMS intervention effects on cognitive function and associated imaging mechanisms.

Data to be recorded for the study include:

Behavioural data: Task-specific behavioural metrics such as accuracy rates and reaction times.

Magnetic resonance imaging data: Acquisition sequences encompass structural imaging, task-state imaging, resting-state imaging, and diffusion tensor imaging.

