3.2 Case Numbers and Grouping Methodology

The study anticipates enrolling 20 subjects with obsessive-compulsive disorder (OCD), all of whom will be assigned to the intervention group for treatment. This is an exploratory clinical study conducted as an open-label trial.

Sample size calculation was performed using G-Power 3.1 with the following parameters:

Effect size d: 1.0

Significance level α : 0.05 (two-tailed)

Power (1- β): 0.95

The calculated minimum sample size required is approximately 16. Considering a 20% clinical attrition rate, 20 participants are planned for enrolment.

IV. Inclusion and Exclusion Criteria

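### Do the paired tests named for inter-group comparisons in section 9.1, and the lack of a named matched test for categorical data, call for a change?

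*Protocol*

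**What the plan says.** Section 3.1 describes the design: "This study constitutes an open-label, prospective, single-centre investigation". Symptoms, cognition and imaging are measured before and after treatment in the same patients. Section 3.2 plans 20 patients, "all of whom will be assigned to the intervention group for treatment". No control arm or second group is defined.

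Section 9.1 nevertheless opens its list of tests with groups in the plural: "Comparisons between groups for general characteristics were analysed using appropriate methods according to indicator type". It continues: "Inter-group comparisons for quantitative data employed paired t-tests (assuming equal variance and normal distribution) or Wilcoxon signed-rank tests based on data distribution". The clause after that reads: "intra-group comparisons used paired t-tests (assuming normal distribution) or Wilcoxon signed-rank tests". The same pair of tests is thus named for both kinds of comparison.

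For nominal data the section gives a general rule, with a fallback in parentheses: "Categorical data will be analysed using chi-square tests or exact probability methods (where chi-square is inappropriate". Ordinal data have their own rule, the signed-rank test or a CMH test. Section 9.2 adds that methods are to be chosen to fit the hypotheses and the experiment.

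**The concern.** Two things look wrong at first reading.

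- **Inter-group tests.** With one group, an inter-group comparison has no object. If subgroups were formed later, a paired test would be invalid for different patients: it needs equal numbers and a meaningful pairing, and independent groups offer neither. The equal-variance condition shows that the sentence mixes two tests. Objective 2 in section II, "To investigate whether provocation techniques for obsessive symptoms can enhance treatment efficacy", is the aim that might draw an analyst towards a contrast between groups, and 9.1 would then point to the wrong test.
- **Categorical data.** In a before-after study a binary variable is measured twice on the same patients. If the categorical rule means Pearson's chi-square with Fisher's test as fallback, it treats the two time points as independent samples and uses the wrong null variance. The error rate of such a test would then differ from the nominal 5%.

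If either rule governed a reported result, that p-value could not be trusted.

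**Working it through.** **1. The plan's own sample size.** Inputs from section 3.2: d = 1.0, two-sided alpha 0.05, power 0.95, attrition 20%. For a paired t-test, power = P(|T| > t(0.975, n−1)), where T is noncentral t with n−1 degrees of freedom and noncentrality d√n.

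- n = 15: noncentrality √15 = 3.87, critical value 2.145, power 0.949.
- n = 16: noncentrality √16 = 4.00, critical value 2.131, power 0.962.

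The minimum is 16, as stated. With attrition, 16/(1 − 0.20) = 20, also as stated. At n = 20 power is 0.989.

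For two independent groups with the same inputs, the noncentrality is d√(n/2) with 2n−2 degrees of freedom. Power is 0.942 at 26 per group and 0.950 at 27, so 54 patients would be needed. The study was therefore sized for the within-patient comparison alone.

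**2. Which clause governs which result.**

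| Result | Type | Rule in 9.1 that applies |
|---|---|---|
| Y-BOCS, before v after (5.1) | quantitative, paired | intra-group clause: paired t or signed-rank; correct |
| HAMD, HAMA and other scale scores (5.2, 5.4) | quantitative, paired | same; correct |
| CGI (5.2) | ordinal, paired | ordinal rule includes signed-rank; correct |
| Binary variable, before v after | none listed in 5.1 to 5.4 | no object |
| Contrast between groups | none defined in 3.1 or 3.2 | no object |

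Adverse events do not fill the fourth row. Section VIII has them recorded at every assessment except baseline, so they yield no paired before-after table.

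**3. What the inter-group rule would do if it were used.** Assume, since the protocol gives no such split, that each patient falls into one of two subgroups with probability 0.5. The sizes are equal, so that a paired test can be computed at all, with probability C(20,10)/2^20 = 0.176 for 20 patients, or C(16,8)/2^16 = 0.196 for 16. For simulated 10 v 10 data with an independent-samples p of 0.05, 95% of arbitrary row orders gave a paired p between about 0.007–0.010 and 0.13–0.14. The rule could not be applied sensibly, but this describes an analysis that the protocol does not plan.

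**4. What the categorical rule would do if read as Pearson.** Exact enumeration of all paired 2×2 tables, assuming a true proportion of 0.5 at both times and a nominal two-sided 5% level, gives these actual levels:

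| n | pre-post correlation | Pearson | exact McNemar | mid-p McNemar |
|---|---|---|---|---|
| 20 | −0.2 | 6.3% | 2.4% | 4.3% |
| 20 | 0 | 4.3% | 2.3% | 4.2% |
| 20 | 0.2 | 2.4% | 1.9% | 3.9% |
| 20 | 0.5 | 0.5% | 0.9% | 2.6% |
| 16 | −0.2 | 7.5% | 2.3% | 4.2% |
| 16 | 0 | 5.2% | 2.0% | 4.0% |
| 16 | 0.2 | 3.0% | 1.5% | 3.5% |
| 16 | 0.5 | 0.7% | 0.5% | 1.7% |

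Pearson's test is not uniformly conservative here: it exceeds 5% at zero correlation with 16 patients and at correlation −0.2 with either number. Exact McNemar has a lower level than Pearson in five of the six rows with correlation 0 or more. McNemar is the right test in principle, but the table does not show that naming it would bring the error rate closer to 5% unless the mid-p form were chosen.

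**The case for a change.** The best case for a change is that the inter-group sentence is an affirmative misstatement, not a detail left to a statistical analysis plan. Section 9.1 itself separates inter-group from intra-group comparisons, so the first cannot easily be read as loose wording for before-after. A later analysis plan that copies the sentence would inherit the error, and rewording costs two or three sentences. That the sentence is wrong stands in full.

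The rest carries less weight. An analyst with one group cannot run the comparison described, and the very next clause names the test that is needed. Objective 2 lacks a comparator by design; no rewording of 9.1 would supply one, so it adds nothing to this point.

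On categorical data, reading the rule as Pearson and Fisher is natural but not forced. McNemar's test is itself a chi-square test with an exact form, and section 9.2 leaves the choice of method to fit the question. Naming the specific matched test is ordinary analysis-plan detail. A responder analysis might be added later, since section I summarises earlier evidence by response rate, but the protocol does not plan one.

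**Conclusion.** The inter-group wording in section 9.1 is a genuine slip, probably carried over from a template for a two-arm trial (an inference; the document does not say so). It has no consequence. The primary Y-BOCS comparison already has a correct paired test, the sample size of 16 (20 after attrition) reproduces exactly on that basis, and no comparison between groups can arise in a one-group design. The categorical point does not hold as an error: the rule is general, does not exclude a matched test, and no listed endpoint would use it.

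No planned estimate, p-value or sample size would change if the text were reworded. The figures for a subgroup contrast or a paired binary variable rest on assumed splits, proportions and correlations, and describe analyses outside the plan. The conclusion rests on the endpoints staying as sections 5.1 to 5.4 list them and on the study staying single-group.

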Subjects may withdraw from the study at any time for any reason. Investigators may withdraw subjects from the study at any time for any reason. If any medical condition or circumstance arises that renders continued participation in the study not in the subject's best interests, the research subject may withdraw from the study. Withdrawal from the study shall not prejudice any benefit to the subject. Following termination, no further data collection shall be conducted from the subject. Reasons for termination or withdrawal shall be documented on the Case Report Form (CRF).

Reasons for study termination include, but are not limited to:

- 1) Death of the subject.
- 2) Loss to follow-up.
- 3) Refusal by the subject to receive further treatment and/or follow-up, accompanied by withdrawal of informed consent.
- 4) Investigator termination of the subject's participation.
- 5) Adverse events (e.g., occurrence of intolerable adverse events or adverse event treatment necessitating withdrawal).
- 6) Serious protocol deviation.
- 7) Subject meeting exclusion criteria (newly emerging or confirmed).

Management of withdrawn subjects:

- 1) All original data for withdrawn subjects shall be retained. If withdrawal occurs due to reason 2, the investigator shall endeavour to contact the subject via multiple channels (e.g., telephone, text message) to ascertain the reason, conducting at least three attempts at follow-up and re-enrolment.
- 2) The timing and reason for trial discontinuation shall be documented in detail on the CRF.
- 3) For subjects withdrawing due to reason 5, adverse events must be appropriately managed, with follow-up continuing until the adverse event (AE) is resolved or stabilised.

VIII. Data Management

This project will utilise Case Report Forms (CRFs) for data recording. The CRF cover page shall display the clinical trial name, study site, subject name abbreviation and code, study start and end dates, and date of each interview to facilitate collation and organisation. The initial interview shall cover: demographic characteristics (pinyin initials, gender, age, ethnicity, etc.), general disease status (diagnosis, duration, etc.), past medical history, prior treatments (medication names, duration, dosage, etc.),

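### Section 9.1 names only two-visit paired tests for a Y-BOCS rated at four visits with 20% expected attrition, so unless missing visits are handled elsewhere, the week 2 and week 4 results rest on those still attending.

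*Protocol*

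**What the plan says.** **Visits.** Section 3.1 has symptoms rated before and after the five-day course, and then: "Symptom follow-up assessments will occur at two weeks post-treatment, with both symptom and cognitive function follow-ups at four weeks post-treatment". That makes four Y-BOCS ratings per subject. Section 5.1 names Y-BOCS as the primary endpoint without a time point.

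**Design and size.** There is one arm, "all of whom will be assigned to the intervention group for treatment". Section 3.2 states "Effect size d: 1.0", two-sided 5% significance and power 0.95, and concludes: "The calculated minimum sample size required is approximately 16". It continues: "Considering a 20% clinical attrition rate, 20 participants are planned for enrolment".

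**Withdrawal.** Section VII collects nothing after a subject's termination, but states: "All original data for withdrawn subjects shall be retained".

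**Analysis.** Section 9.1 says "intra-group comparisons used paired t-tests (assuming normal distribution) or Wilcoxon signed-rank tests". With no second arm, this is the operative method for every quantitative efficacy scale. The protocol names no repeated-measures model and no imputation. Section 9.2 leaves methods open, but in a paragraph on imaging, electrophysiological and behavioural data.

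**The concern.** A paired test takes two visits at a time and uses a subject only if both values exist. A subject rated at the end of treatment who then leaves adds nothing to the week 2 or week 4 result. Yet the retained end-of-treatment rating is informative about the rating that is missing.

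If subjects leave for reasons related to their early response, those still attending at week 4 are a selected group, and their mean change is not that of the treated group. There is no control arm in which similar losses could partly offset this, so any distortion passes straight into the reported Y-BOCS fall. The first objective is efficacy, so the size of that fall matters. Part of the information needed to reduce the distortion is already collected, and the named test does not use it.

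**Working it through.** **1. The plan's own figure.** Inputs from section 3.2: d = 1.0 (read as mean change divided by SD of change), two-sided α = 0.05, power 0.95, attrition 20%. Power of a paired t-test comes from the noncentral t distribution with n − 1 degrees of freedom and noncentrality d√n.

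- n = 15: power 0.949, just short.
- n = 16: noncentrality 1.0 × √16 = 4, power 0.962.
- Allowance for attrition: 16 / (1 − 0.20) = 20.

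Both 16 and 20 reproduce. If 4 of 20 are lost, 16 remain and power is still 0.962 at d = 1.0. Planned power is not the problem.

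**2. Upper case: the four poorest early responders leave (4/20 = 20%).** Let the change to end of treatment be normal with mean −1 and SD 1, in units of SD of change. Removing the worst 20% moves the mean of those who remain by φ(z₀.₈)/0.8 = 0.280/0.8 = 0.35 SD. If the end-of-treatment and week 4 changes correlate at ρ, the week 4 completer mean moves by 0.35ρ:

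- ρ = 0.5: 0.35 × 0.5 = 0.175 SD
- ρ = 0.85: 0.35 × 0.85 = 0.30 SD

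The documents do not give ρ, so this range is assumed. If the SD of change were 6 points (also assumed), this would be 0.175 × 6 = 1.05 to 0.30 × 6 = 1.8 points on a true fall of 6.

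**3. Graded loss.** Simulation with 400,000 subjects, true week 4 change −1.00 SD, 20% missing at week 4, ρ from 0.5 to 0.9. In the two response-related rows the logistic dropout slope is 1.5 per SD (assumed).

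| Loss depends on | Completers (paired) | Likelihood estimate using end-of-treatment ratings |
|---|---|---|
| Nothing (random) | −1.00 | −1.00 |
| Observed end-of-treatment change | −1.11 to −1.21 | −1.00 |
| Unseen week 4 change | −1.22 to −1.23 | −1.05 to −1.18 |

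The second row is an overstatement of about 0.1 to 0.2 SD, which the likelihood estimate removes. In the third row the likelihood estimate is less biased than the paired one but still biased.

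**4. Which comparison is exposed.** In these scenarios loss follows the end-of-treatment rating, so the baseline to end-of-treatment test has no missing values and no attrition bias. Section 3.2 gives one overall 20%, not a rate per visit, so the full figure fits week 4 best and week 2 less well.

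**The case against.** **Section 9.1 does not prescribe a completer analysis.** A reader might infer that it does. It names a test; it defines no analysis set, gives no missing-data rule and does not say which Y-BOCS visits are compared. A paired test can be run on imputed values, and a statistical analysis plan not available here may supply the rule. This stands, and it makes the point conditional. What remains is that the only method named cannot, by itself, use the retained ratings.

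**Section 3.2 does not say that 16 will be analysed.** That too might be inferred from 16 inflated to 20. Inflating for attrition protects power; it does not define who is analysed. This stands.

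**Nothing shows that poor responders leave.** The reasons listed in section VII, which are not exhaustive, do not include lack of efficacy, and treatment is over before week 2. Loss could be random, giving no bias, or could favour good responders, reversing it. This stands: the direction is an assumption.

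**The bias is modest for so small a study.** The graded figure of 0.11 to 0.21 SD is below the standard error of a mean of 16, which is 1/√16 = 0.25 SD. This is true, but the standard error is shown by the confidence interval and the bias is not.

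**A mixed model is no cure-all.** It leaves bias when loss depends on unseen scores. An unstructured four-visit covariance has 4 × 5 / 2 = 10 parameters for 20 subjects. It also lacks the signed-rank option for non-normal data. These points call for a stated fallback and a retained sensitivity analysis; they do not favour paired tests alone.

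**Conclusion.** The point holds in a limited, conditional form. Unless missing visits are handled elsewhere, the week 2 and week 4 comparisons use only subjects still attending and set aside ratings the trial already holds. Under assumed loss of poor early responders, the week 4 fall is overstated by about 0.1 to 0.2 SD of change if loss is graded and 0.2 to 0.3 SD if exactly the four poorest leave, which is a bound and not an expectation. Under random loss there is no bias. These sizes rest on assumed correlations between visits and an assumed dropout strength.

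It would go too far to say that the trial's main result is biased or its power eroded: the end-of-treatment comparison and the sample size calculation are largely untouched. This is a cheap improvement to the analysis, not the correction of an invalid test.

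**What to change.** In section 9.1, analyse Y-BOCS and the other scales rated at several visits with one linear mixed model each:

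- SPSS MIXED with REML, visit as a factor, on all treated subjects with a baseline rating;
- unstructured within-subject covariance, with a simpler structure named in advance if it does not converge;
- Satterthwaite degrees of freedom;
- estimated mean change from baseline with a 95% confidence interval at each visit.

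Keep the paired t-test or signed-rank test as a sensitivity analysis; this also covers clear departures from normality.

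Cost: one paragraph, with no new software, data or subjects. Downside: the model assumes approximate normality and that loss depends only on observed ratings. If loss depends on unobserved scores, it reduces the bias and does not remove it; the text should say so.

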9.2 Statistical Analysis of Research Data

Magnetic resonance data will be analysed using the SPM toolkit based on MATLAB. Electrophysiological data will be analysed using the fieldtrip toolkit based on MATLAB. Behavioural data will be analysed using MATLAB. Statistical methods will be selected according to research hypotheses and experimental requirements. Statistical software utilised will include MATLAB and SPSS. The primary focus of the study is to compare changes in brain activity (magnetic resonance, electrophysiological) and behaviourally measured cognitive alterations before and after transcranial magnetic stimulation or electrical stimulation.

X. Conflict of Interest

There are no relevant conflicts of interest for this study.

XI. Privacy and Confidentiality

This study will implement stringent privacy protection policies. All information pertaining to this project and its collaborations will be securely safeguarded. No personally identifiable information concerning participants will be disclosed to any external parties under any circumstances. Even if study results are published, participants' personal details will remain confidential.

Participants retain the right to access their personal information and the final research findings. Personal data will be protected throughout all stages of collection, storage, and application (including analysis and comparison).

PI's Signature:

Date:

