5.1 Primary Endpoint

Obsessive-compulsive symptom severity: Yale-Brown Obsessive Compulsive Scale (Y-BOCS)

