5.4 Exploratory Endpoints

Beck Depression Inventory (BDI)

Chinese Version State-Trait Anxiety Inventory (STAI-S, STAI-T)

Chinese Version of the Obsessive-Compulsive Inventory (Revised) (OCI-R)

Intolerance of Uncertainty Scale (IUS-12)

Intolerance of Uncertainty Questionnaire (IUI-A, IUI-B)

Stress Perception Scale

Snaith-Hamilton Pleasure Scale (SHAPS)

Aphasia Evaluation Scale (Self-Report Version) (AES-S)

Physiological Data: Imaging and EEG require signal-to-noise ratios within acceptable ranges. Excessive head motion and motion artefacts may compromise data quality.

Data significantly affected (e.g., imaging head motion impacting image clarity, electrophysiological artefacts exceeding 20% of data) will be excluded.

Cognitive Behavioural Data.

All behavioural data exceeding three standard deviations above or below the mean will be excluded to prevent statistical bias.

VI. Adverse Event Collection and Reporting

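### Section 9.2 makes change in brain activity and cognition the study's primary focus, and 3.1 states a cognitive aim, although Y-BOCS is the only primary endpoint (5.1) and those outcomes are exploratory (5.4)

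*Protocol*

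**What the plan says.** Section V of the protocol ranks the endpoints. Section 5.1 has one entry: "Obsessive-compulsive symptom severity: Yale-Brown Obsessive Compulsive Scale (Y-BOCS"). Section 5.4, the exploratory list, contains "Physiological Data: Imaging and EEG require signal-to-noise ratios within acceptable ranges" and, as a separate entry, "Cognitive Behavioural Data".

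Section II agrees with that ranking. Objective 1 is "To validate the efficacy of 20Hz rTMS targeting the right IFC in treating treatment-resistant obsessive-compulsive disorder"; objective 3 is "To explore the effects of transcranial magnetic stimulation on cognitive function in OCD patients" and the possible physiological mechanisms.

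Section 9.2, which closes the statistical part, says otherwise: "The primary focus of the study is to compare changes in brain activity (magnetic resonance, electrophysiological) and behaviourally measured cognitive alterations" before and after stimulation. Y-BOCS is named in neither 9.1 nor 9.2. Section 3.1 points the same way as 9.2, giving the regulation of cognition by non-invasive intervention as what the study sets out to investigate.

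Two further provisions matter. Section 9.1 sets two-sided tests with p < 0.05 as the criterion throughout. Section 3.2 calculates a sample size (d = 1.0, two-sided 0.05, power 0.95, about 16 patients, 20 with attrition) without naming an endpoint, visit or test.

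**The concern.** The same outcomes are exploratory in Section V and the primary focus of the whole study in 9.2. Whoever writes the analysis or the report could follow either place and claim the protocol's support.

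The choice has consequences because what 9.2 elevates is not a single outcome. Section 3.1 lists structural, task-based, resting-state and diffusion imaging, and a broad cognitive battery: "These tasks primarily evaluate working memory whilst also assessing attention, learning and memory, executive control, reasoning ability", followed by decision-making under risk, affective decisions and emotional awareness. No single imaging or cognitive measure is singled out as the one to test. With p < 0.05 applied to each test, some nominally significant change is fairly likely even if nothing changed, and 9.2 would let it stand as the main finding. The outcome that 5.1 makes primary could then be reported in second place.

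**Working it through.** **1. The plan's own figure.** Inputs from 3.2: d = 1.0, two-sided α = 0.05, power 0.95, 20% attrition. For one paired t-test, power comes from the noncentral t distribution with n − 1 degrees of freedom and noncentrality d√n.

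- n = 15: noncentrality √15 = 3.87, power 0.949, just short of 0.95.
- n = 16: noncentrality √16 = 4.00, power 0.962.
- Attrition: 16 / (1 − 0.20) = 20.

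Both stated numbers reproduce, so 3.2 is consistent with a single before-after test. It does not say which one.

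**2. The rankings side by side.**

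| Place | Y-BOCS / efficacy | Imaging, EEG, cognition |
|---|---|---|
| Section II | Objective 1, to validate | Objective 3, to explore |
| 3.1, aim sentence | not named | cognition is the stated aim |
| 5.1 | only primary endpoint | absent |
| 5.4 | absent (only a different OCD scale, OCI-R, is listed) | exploratory |
| 9.2 | not named | primary focus of the study |

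Sections II and V agree with each other. The sentence in 9.2 contradicts them, and the aim sentence in 3.1 leans the same way as 9.2.

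**3. Illustration of what following 9.2 could mean.** Take the eight cognitive domains of 3.1 (five in the quoted list and three after it), one score per domain, one paired t-test each at two-sided 0.05, 16 patients and no true change. With independent scores, the chance of at least one p < 0.05 is 1 − 0.95^8 = 1 − 0.6634 = 0.337. With equally correlated change scores, simulation (200,000 trials per row) gives:

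| Assumed correlation | n = 16 | n = 20 |
|---|---|---|
| 0 | 0.336 | 0.339 |
| 0.3 | 0.305 | 0.300 |
| 0.5 | 0.259 | 0.257 |
| 0.7 | 0.200 | 0.198 |

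The range is about 20% to 34%, before any imaging or EEG test is counted, against 5% for one pre-named test. The protocol gives no correlations and does not fix one score per domain; both are assumptions.

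**The case against.** The strongest defence is that a primary focus is not a primary endpoint. Section 5.1 is clear, the rest of 9.2 deals only with imaging, electrophysiological and behavioural data, the general within-group tests of 9.1 already cover a scale such as Y-BOCS, 3.2 calls the study exploratory, and a separate SAP may set out the hierarchy.

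Part of this stands. Section V does rank the endpoints, a test for Y-BOCS can be found in 9.1, and no number in the protocol is wrong. The rest does not remove the conflict. The 9.2 sentence speaks of the study, not of the imaging data, and 3.1 shows that the emphasis is not an isolated slip. An SAP can supply missing detail, but here the protocol states two incompatible rankings and an SAP could cite either. Exploratory or not, objective 1 is worded as validation and 3.2 fixes α and power, so one test should be identifiable.

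The eight-domain figure also has limits. Section 3.1 says "Participants will undergo tailored cognitive assessments based on" each patient's clinical picture, so it is not established that every patient completes all eight domains, and working memory is named as the main target. The figure shows the kind of risk; it does not estimate this trial's error rate.

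A reader might also infer that Y-BOCS may be declared positive at any of its three post-baseline assessments (end of treatment, two weeks, four weeks), so that its own 5% level fails. If that were the rule, the error would be about 8.6% to 12.8% at n = 16 for assumed equal correlations of 0.9 to 0.5. But no section states an any-visit rule, and the choice of visit is a detail that an SAP could hold.

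**Conclusion.** The contradiction is real. Sections 9.2 and 3.1 give brain activity and cognition a standing that 5.1, 5.4 and the objectives deny them, and the conflict lies in the section that governs the analysis. It should be corrected before data are seen, because it decides which result may be reported as the main one. This conclusion rests on the text alone. The 20% to 34% is an illustration, conditional on eight tests in 16 patients, one score per domain and correlations of 0.7 to 0.

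Two stronger readings are not supported. The trial does not lack a primary endpoint: 5.1 names one. The sample size is not wrong: 16 and 20 both reproduce. That 3.2 was calculated for Y-BOCS is plausible, but the protocol does not say so. The unnamed Y-BOCS visit is a side note that the same rewording settles.

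**What to change.** Replace the sentence in 9.2 with wording such as:

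> The primary analysis is the change in Y-BOCS total score from baseline to [one post-treatment visit, named by the sponsor before data are seen], tested once at two-sided 0.05 with the paired test in 9.1. Y-BOCS at the other visits is secondary. Imaging, EEG and cognitive outcomes are exploratory (5.4) and are not reported as the primary result.

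Align the aim sentence in 3.1 with this ranking. The sponsor should confirm that the calculation in 3.2 refers to this Y-BOCS test and, if so, say so there.

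Two editorial items can be tidied in the same amendment but carry no weight here: 3.1's list of recorded data does not mention EEG, and 3.1 and 9.2 refer to electrical stimulation although the intervention is rTMS.

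The cost is protocol wording. The 16 evaluable and 20 enrolled patients do not change. The downside is that imaging and cognitive outcomes, and Y-BOCS at the visits not chosen, lose any claim to primary status. The rewording does not remove the limits of an uncontrolled open-label before-after comparison.
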